2. STRESS VARIABLES

2.1 Academic stress questionnaire at university (CEAU).

This questionnaire prepared by García - Ros & Pérez - González (2012), (ANNEX 05) assesses possible stressful

situations in the university environment and consists of a total of 21 items. The participants' responses indicate the level of perceived stress in each situation using a Likert-type response scale with 5 options ranging from “no stress” (1) to “a lot of stress” (5). The internal consistency of this instrument, in this study, has a .819 once Cronbach's α has been analyzed.

This questionnaire is divided into 4 subscales, which are:

- Academic obligations (OA): consists of 8 items (1, 5, 7, 9, 10, 11, 14 and 15) that assess the level of stress generated in students by carrying out academic work and exams, the lack of time to develop activities, academic overload, performing required work, excess responsibilities and study-related activities. Its internal consistency is .675 using Cronbach's α .
- Record and future prospects (EF): provided with 6 items (16, 17, 18, 19, 20, 21) that, like the previous one, measure the stress generated by the anticipation of problematic situations or future academic situations, such as completing the studies within the stipulated deadlines, obtaining high grades, maintaining or obtaining a scholarship, the choice of subjects and itineraries during the career and family pressure to obtain good results. Its internal consistency in this study is .691 using Cronbach's α .
- Interpersonal difficulties (ID): using 4 items (6, 8, 12, 13) determines the level of stress that can produce problems or conflicts with classmates and teachers, as well as that related to competitiveness with peers. Its internal consistency is .758 through the analysis of Cronbach's α .
- Expression and communication of own ideas (EC): through 3 items (2, 3, 4) stress is evaluated in the moments that students are required to present and express their own ideas in the classroom in the presence of all their colleagues. Its internal consistency is .725 according to Cronbach's α .

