2.2 Academic Stress Coping Scale (A-CEA)

The coping scale, known as A-CEA (González Cabanach et al., 2010), is a subscale of the CEA questionnaire, an instrument made up of three scales, which is used to assess academic stressors (E-CEA), stress responses (R-CEA) and stress coping strategies (A-CEA). (ANNEX 06).

The A-CEA scale is made up of 23 items, formulated to evaluate the cognitive and behavioral strategies used by the student when facing situations of academic stress. It is a scale with Likert-type responses to each item, in which the student can choose between five options: Never (1), Sometime (2), Many times (3), Many times (4) and Always (5). The reliability of the A-CEA scale has a general Cronbach coefficient for this study of .885. In turn, this coping scale is divided into 3 factors that are specified below:

- Factor 1. Positive Reevaluation: This dimension groups nine items (1, 3, 4, 5, 6, 14, 17, 18 and 19) that present different ways of coping aimed at creating a new positive meaning about the problem or academic difficulty. This factor underlines its active and positive character in propositions such as “When I face a problematic situation the night before the exam I try to think that I am prepared to do it well” or “When I face a complicated situation, in general, I try not to give it importance to the problems”. Its internal consistency according to Cronbach's α is .668.
- Factor 2. Search for Social Support: It includes seven items (2, 8, 10, 13, 20, 21 and 23) to evaluate an active and behavioral type of coping, based on the student's search for information and advice, as social support to the problem, and also of understanding on the part of other people, as emotional support with what he experiences. Its internal consistency according to Cronbach's α is .727.
- Factor 3. Planning and management of personal resources: It includes seven items (7, 9, 11, 12, 15, 16 and 22) that refer to the activation of strategies based on analysis and reasoning to change the problem situation, and that denote a type of behavioral and active coping. Its internal consistency according to Cronbach's α is .741 for this study.

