2.3 Sociodemographic variables questionnaire

A third questionnaire (ANNEX 03) to collect necessary information on sociodemographic variables such as age, gender, place of residence and type of home. This questionnaire also aims to collect some data referring to their academic life, such as the average grade for access to the university and the degree completed. The ad-

hoc questionnaire consists of a total of 11 items and all questions are made in a clear and concise manner so that the answer is free from ambiguity.

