3. ACADEMIC PERFORMANCE

The final average grade of the first academic semester will be analyzed comparing by groups.

To dispense the questionnaires, a computer tool will be designed through the Google Forms platform, which will allow the creation and distribution of said questionnaires digitally, which will facilitate their dissemination and subsequent coding. The link to said questionnaire will be sent to the participants by email, which will be completed electronically without the need to contact the researcher. Once completed, the results will be automatically sent to the main researcher, subsequently being encoded in a statistical database.

In order to compare the individual results of the PRE and POST intervention questionnaires, they will be identified with the identification code of the participants, without thus making it possible to identify the subjects.

STATISTICAL ANALYSIS PLAN OF THE RESULTS

For the coding and analysis of the data, the statistical program IBM® SPSS Statistics version 22 will be used. For the treatment of categorical variables, tables of absolute and relative frequencies will be made, which will be analyzed using Pearson's Chi-square.

In the case of quantitative variables, the mean and standard deviation will be obtained as the measures of central tendency and dispersion index. The Kolmogorov-Smirnov test will be performed to check the normality of the distribution in the event that the sample obtained is the expected one (greater than 30 individuals). If the distribution is normal, parametric tests will be performed to assess differences between groups. Statistically significant differences will be sought between the quantitative variables of the groups by means of a student's t test for independent measures. and repeated measures ANOVA to compare the measures collected at different times in the same group. If the population does not follow a normal distribution of the variable under study, non-parametric tests will be performed to determine the differences between groups. Friedman's test for paired samples and Kruskal Wallis's test for independent samples. In all cases, a 95% confidence interval and a significance level less than or equal to 0.05 will be established.

FORECAST OF POSSIBLE SIDE EFFECTS THAT MAY OCCUR

Anticipation of possible risks / damages and mechanisms to reduce harm or distress to a minimum

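### The between-arm tests give no stated role to the PRE value, university or access grade; an ANCOVA on data already collected would usually gain precision at almost no cost

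*Combined protocol and SAP*

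**What the plan says.** The section on study variables sets three measurement times: PRE, POST and one month later. The Statistical Analysis Plan of the Results then gives two kinds of test for quantitative variables.

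- Between arms: "differences will be sought between the quantitative variables of the groups by means of a student's t test for independent measures".
- Over time: "repeated measures ANOVA to compare the measures collected at different times in the same group".

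If a Kolmogorov-Smirnov test rejects normality, the substitutes are "Friedman's test for paired samples and Kruskal Wallis's test for independent samples".

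The one stated use of PRE together with POST is record linkage by participant code, introduced with "In order to compare the individual results of the PRE and POST intervention questionnaires". No between-arm estimator is attached to it. Random Assignment balances the arms within each university, but the analysis section does not mention university.

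The semester grade has its own sentence: "The final average grade of the first academic semester will be analyzed comparing by groups". The sociodemographic questionnaire collects "the average grade for access to the university". The general rules would let that grade be summarised or compared by arm, but nothing makes it a covariate.

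For the stress scales, the CEAU description says "This questionnaire is divided into 4 subscales" and the A-CEA description says "this coping scale is divided into 3 factors". The analysis section does not say which of these scores is tested.

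**The concern.** The study plans 80 participants, about 40 per arm, and calls itself a pilot, so precision is scarce. A student's PRE score often predicts the POST score, and the entry grade may well predict the semester grade. Both are already in the database. An unadjusted comparison leaves that predictable variation in the error term and widens the interval around the NESA effect. University was built into the allocation and can be carried into the model at little cost.

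The longitudinal tests do not fill the gap. A repeated measures ANOVA or Friedman test run inside one arm estimates change in that arm, which mixes any NESA effect with the exam calendar and regression to the mean. It does not estimate a difference between arms.

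**Working it through.** **The plan's own figure.** There is no power calculation to reproduce: 80 is a pilot number without an effect size, SD or power. The participant codes agree with it (4 universities x 20 = 80).

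**Inputs from the documents.** N = 80; arms balanced within university, read as 40 per arm and 10 per arm per university; significance level 0.05, taken as two-sided.

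**Assumed inputs.** A true difference of 0.5 SD, a PRE-POST correlation r from 0 to 0.7, no eliminations and, at first, no university effect.

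**POST t-test.** In SD units the standard error is sqrt(2/40) = 0.2236. The noncentrality is 0.5/0.2236 = 2.236 on 78 df, which gives power of 59.8%.

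**ANCOVA with PRE and university.** Residual df are 80 - 2 (intercept and arm) - 1 (PRE) - 3 (university) = 74. The variance of the arm effect is (2/40)(1 - r²)(1 + F/74). F follows an F(1,74) distribution and represents chance imbalance in PRE; power is averaged over it.

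**Change-score t-test**, which the wording does not exclude. The variance is (2/40) x 2(1 - r) on 78 df.

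| r | POST t-test | Change-score t-test | ANCOVA |
|---|---|---|---|
| 0 | 59.8% | 34.5% | 59.2% |
| 0.1 | 59.8% | 37.7% | 59.6% |
| 0.3 | 59.8% | 46.3% | 63.2% |
| 0.5 | 59.8% | 59.8% | 71.6% |
| 0.7 | 59.8% | 81.4% | 86.6% |

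ANCOVA equals the POST t-test at r of about 0.12. At r = 0 it loses 59.8 - 59.2 = 0.6 points, mostly from chance imbalance in PRE. With three universities (75 df) the figures change by less than 0.1 point. The 95% CI half-width is 0.445 SD for the t-test and 0.428, 0.389 and 0.320 SD for ANCOVA at r = 0.3, 0.5 and 0.7.

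**Unequal arms.** If eliminations left 32 NESA and 40 control, unrelated to outcome (an assumption), the t-test would have 54.7% power and ANCOVA 58.0%, 66.3% and 82.3% at r = 0.3, 0.5 and 0.7.

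**University.** With an assumed 10% of variance between universities and r = 0.5, simulated power is 61.2% for the t-test and 76.2% for the full model. With no arm effect, the t-test rejects in 4.3% of trials and the full model in 5.1%. Ignoring university therefore costs power and does not inflate false positives.

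**Semester grade.** The same formula applies, with the access grade in place of PRE. At assumed correlations of 0.3 and 0.5, power is 63.2% and 71.6%, against 59.8% unadjusted.

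**Within-arm tests.** A simulation used paired PRE-POST tests as a two-visit stand-in for the within-arm ANOVA. With no arm effect but a common 0.3 SD shift over time, only the NESA arm was significant in about 22% to 24% of trials.

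**The case against.** The strongest reply is that nothing here is wrong. A randomised t-test is valid, a pilot has no power target to miss, and every gain above rests on an assumed effect and correlation. That stands, and it limits the point to a cheap improvement in precision. It does not remove the point, because the plan still tests at 0.05 and the adjustment needs no new data.

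A reader might infer more, in four ways that the documents do not support.

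- *That no between-arm test exists, or that efficacy will be read from within-arm change.* A between-arm test is planned, and the plan does not commit to reading within-arm results as efficacy.
- *That PRE is excluded.* The plan links PRE and POST to compare them. It simply does not say how PRE enters the comparison of arms.
- *That the missing group-by-time term is itself the defect.* With two arms and only PRE and POST, that interaction is the change-score t-test, which at r = 0.3 has less power (46.3%) than the plain t-test (59.8%).
- *That the open visit and score will produce many false positives.* For one score, free choice among raw or change at POST or one month gives at least one p < 0.05 in about 16% of null trials if the POST to one-month correlation equals r. It gives 13% to 15% if that correlation is 0.8 (r from 0.3 to 0.7). These are upper bounds that require selective reporting, which the plan does not announce. Choosing among subscales as well would raise them, but CEAU and A-CEA serve the secondary stress objective, not the sleep objective.

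The unnamed visit and score are mainly missing detail, best supplied when the model is written.

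**Conclusion.** The point holds as a loss of precision that is cheap to recover, and should be fixed. The omission is plain in the text. Its size is less certain: at an assumed 0.5 SD difference with 40 per arm, adjustment adds 3.4, 11.8 and 26.8 points of power at correlations of 0.3, 0.5 and 0.7. It adds nothing at about 0.12 or below when universities do not differ. The documents give neither the effect size nor the correlation. No bias and no invalid test is claimed.

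**What to change.** Amend the Statistical Analysis Plan of the Results as follows.

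1. For each repeatedly measured outcome, make the between-arm analysis an ANCOVA of the POST value on arm, PRE value and university, reporting the adjusted difference with its 95% CI.
2. State that this replaces the Kolmogorov-Smirnov-driven choice between the t-test and Kruskal-Wallis, with a rank-based or bootstrap version only as a sensitivity analysis.
3. Analyse the one-month value by the same model, as secondary.
4. Adjust the semester grade for access grade and university.
5. Name the score that carries the sleep conclusion, and treat CEAU and A-CEA as secondary.
6. Label within-arm tests descriptive.

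Before coding the university term, reconcile the abstract's three universities with the four in the scope and random assignment sections. Who is analysed under the elimination rule is a separate question that this change does not settle.

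The cost is SAP wording plus that reconciliation. The model needs no new data and is a standard procedure. It uses four residual degrees of freedom (78 to 74) with four universities, or three (78 to 75) with three, and loses about 0.6 points of power if the covariates explain nothing.

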The correct application of the NXSIGNAL® device, as well as an adequate programming, is of vital importance for the fulfillment of the objective. General guidelines will be established, which must always be followed with the application of NESA microcurrents, and specific guidelines for this particular study, in order to obtain a sample as homogeneous as possible and bring the programming of the device closer to the objective to be pursued. in the clinical trial. General guidelines for the application of NXSIGNAL®.

- The skin must be clean, free of creams and grease, so it will be necessary to clean with alcohol or similar. The device's gloves and socks will be placed in accordance with the established protocols, paying attention to the location of each semi-electrode in its anatomical position. The device has a color system to determine the location of each cable.
- The directing electrode will be located with the skin equally clean, and will be essential for the operation of the technology.
- The use of electronic devices by the patient, less than one meter away, is contraindicated in order to optimize their use. The electrodes are connected to the control console and the targeting electrode located on the intervertebral area between C7 and T1 (cervical area) and will follow the central treatment pattern with the following combination:

Programación X-Signal Estudio Calidad Sueño en Estudiantes

[figure not shown]

Figure 4. The numbers located vertically to the left of the image represent the number of sessions. The central blocks refer to the programs and the application time and in the vertical right column the type of central application of the targeting electrode is defined, located in the cervical area C7.

The default schedule is based on the goals set in this study. The main objective is to improve the quality of sleep. The secondary objectives are to correlate with improving perception of stress and academic performance.

Group 2: Control group without NESASIGNAL[®] application

The same protocol for the analysis of variables is followed, but without performing any type of treatment with the NESASIGNAL device.

DEFINITION OF THE STUDY VARIABLES AND MEASUREMENT INDICATORS:

The variables will be measured before the start of the intervention (PRE), at the end of the intervention (POST) and one month after the end of the study.

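### No stress score or visit is designated and every test uses 0.05, so testing all nine stress scores at two visits would inflate the false-positive rate (minor point, secondary objective)

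*Combined protocol and SAP*

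**What the plan says.** All references are to the combined protocol and SAP.

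- **Secondary objectives.** The stress objective is worded as a correlation with improvement in stress perception. It names no score and no visit.
- **Section 2.1 (CEAU).** A 21-item academic stress questionnaire: "This questionnaire is divided into 4 subscales, which are" then listed with their items and a Cronbach alpha each.
- **Section 2.2 (A-CEA).** A 23-item coping questionnaire, also filed under stress variables: "this coping scale is divided into 3 factors that are specified below", again with items and alphas.
- **Definition of the study variables.** Measurement is before the intervention, then "at the end of the intervention (POST) and one month after the end of the study".
- **Statistical analysis plan.** "Statistically significant differences will be sought between the quantitative variables of the groups by means of a student's t test for independent measures", with a non-parametric alternative if normality fails. It also plans "repeated measures ANOVA to compare the measures collected at different times in the same group". One level covers all of these: "In all cases, a 95% confidence interval and a significance level less than or equal to 0.05 will be established". There is no test hierarchy, no multiplicity adjustment and no exploratory label.
- **Calculation of the sample.** 80 participants, described as a pilot, with no power calculation.

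**The concern.** A 0.05 level controls the error of one test. Here it is applied separately to every comparison, and nothing says in advance which comparison answers the stress question. With several overlapping scores and two visits, the analyst can find a significant stress difference by chance well above the stated rate and has no written rule for setting it aside. Naming a primary sleep variable would not cure this, because the stress comparisons would still be uncontrolled. At stake is whether a reported effect on stress, which the abstract hopes to show, can be read at the level the plan states.

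**Working it through.** **Inputs from the document.** Level 0.05 per test (sidedness not stated; two-sided assumed). 80 participants with balanced allocation, so 40 per arm. Alphas: CEAU total .819, subscales .675 (8 items), .691 (6), .758 (4), .725 (3); A-CEA total .885, factors .668 (9), .727 (7), .741 (7).

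**Assumed, because not given.** Correlation between the two questionnaires 0 to 0.3; correlation between the two visits 0.3 to 0.9.

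**1. The plan's own figure.** The only one is 0.05 per test. For one test the false-positive rate is 5%, of which 2.5% is in the favourable direction. No family-wise rate or power is stated, so there is nothing further to reproduce.

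**2. Count.** CEAU 1 + 4 = 5 scores; A-CEA 1 + 3 = 4; 5 + 4 = 9. Over two visits, 9 × 2 = 18 between-arm tests at most.

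**3. Independence.** Any significant result: 1 − 0.95^18 = 0.603. Favourable only: 1 − 0.975^18 = 0.366. Totals contain their own subscales and the same students are measured twice, so the real rate is lower.

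**4. Correlations implied by the alphas.** The mean inter-item correlation is r = α / (k − α(k − 1)). For the CEAU total: .819 / (21 − .819 × 20) = 0.177. For its subscales: 0.206, 0.272, 0.439 and 0.468. There are 210 item pairs, 28 + 15 + 6 + 3 = 52 of them within subscales, leaving 158 across. The mean cross-subscale item correlation is (210 × 0.1773 − 13.88) / 158 = 0.148, where 13.88 is the sum over within-subscale pairs. Two subscales then correlate k₁k₂ × 0.148 / (s₁s₂), with s = √(k + k(k − 1)r). This gives 0.24 to 0.43 between CEAU subscales. The same steps give 0.67 to 0.80 between A-CEA factors.

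**5. Simulation with no true effect.** 40,000 trials per setting, 40 per arm, two-sided t tests at 0.05, totals built from their subscales, scores oriented so that a positive difference favours NESA.

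| Tests performed | Independent: any (favourable) | Correlated: any | Correlated: favourable |
|---|---|---|---|
| 9 scores × 2 visits (18) | 60.3% (36.6%) | 33–45% | 17–24% |
| 9 scores, POST only (9) | 37.0% (20.4%) | 25–27% | 13–14% |
| CEAU only, 5 scores × 2 visits (10) | 40.1% (22.4%) | 24–31% | 12–16% |
| Two totals × 2 visits (4) | 18.5% (9.6%) | 13–18% | 6–9% |
| CEAU total × 2 visits (2) | 9.8% (4.9%) | 7–10% | 3.5–4.8% |
| One score, one visit (1) | 5% (2.5%) | 5% | 2.5% |

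**6. Sensitivity.** Replacing the alpha-derived correlations by 0.3–0.5 within each questionnaire, 0.1–0.3 between them and 0.5–0.7 between visits gives 40–48% for the 18 tests, up to 26% favourable. The two sets together give 33–48% and 17–26%. Much stronger correlations (0.8 within, 0.6 between, 0.9 between visits) would bring the 18-test figure down to 24% (12% favourable), but the CEAU alphas do not support 0.8 within that questionnaire.

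The within-arm repeated-measures tests are not counted. They would add further chances.

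**The case against.** The strongest reply is that 18 tests is a ceiling and not the plan. Sections 2.1 and 2.2 describe how the questionnaires are built; the analysis plan never says that subscales will be tested. The section on handling the questionnaires speaks of comparing PRE with POST and does not mention the one-month visit there, although that visit is scheduled. The A-CEA measures coping strategies, so a change in one of its factors is not plainly a change in perceived stress. The objective is secondary, in a pilot, and is worded as a correlation. All of this stands. It lowers the severity and is why the narrower readings are shown. It does not remove the gap, because nothing in the plan restricts the stress tests to fewer scores or to one visit.

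A reader might infer something stronger: that the plan produces a false finding of improved stress in 40–60% of trials, and that any one significant score would count as success. The document does not support this. The 60% needs 18 independent tests, which overlapping scores and repeated visits rule out. Rates of 40% and above count significance in either direction, including worse stress under NESA. No passage states that any single score would suffice; the abstract expresses a hope, not a decision rule.

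**Conclusion.** The point holds at minor severity. The plan applies an unadjusted 0.05 to the between-arm stress comparisons without designating a score or visit. The 33–48% (17–26% favourable) is conditional on all nine scores being tested at both visits, on two-sided tests and on correlations that are partly derived from the reported alphas and partly assumed. Restricting the family to the CEAU, the instrument closest to stress perception, still leaves 24–31% (12–16% favourable). Only if the CEAU total alone is tested does the inflation become modest, and the plan does not say that. The 60% should be cited only as the independence ceiling.

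**What to change.** Add to the statistical analysis plan:

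1. The between-arm comparison for stress perception has one key test, the CEAU total at POST. CEAU subscales, all A-CEA scores (coping) and all one-month stress scores are exploratory and are reported as estimates with 95% confidence intervals, without significance claims.
2. The correlation objective is analysed separately, as an estimated correlation between change in sleep quality and change in CEAU total. The objective does not say what is to be correlated with stress, so the investigators should confirm this reading.

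With one key test the rate returns to 5% (2.5% favourable). The cost is a few sentences, with no new data, visits or participants. The downside is that an effect confined to one subscale, or appearing only at one month, could be described but not claimed. The change should be made before analysis: the database is to be erased after a coding and analysis period estimated at two months, which leaves little room for later re-analysis.

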Randomized clinical trial with passive control, triple blind (for the patient, the physiotherapist applying the technique and evaluator), with a parallel and multicenter design. The study will have two arms, the intervention group will undergo neuromodulation treatment with the NESA XSIGNAL® device and the control group will not carry out any intervention, but both will be evaluated for the same variables at the same times.

SCOPE AND STUDY POPULATION:

Multicenter study whose collaborating entities correspond to the University of Las Palmas de Gran Canaria, Alfonso X el Sabio University, the Pontifical University of Salamanca and the University of Alcalá de Henares. The study population will be students from the collaborating universities, corresponding to first-year health sciences degrees. For the selection of the sample, a non-probabilistic convenience sampling will be carried out, which allows selecting those accessible cases that agree to be included.

CALCULATION OF THE SAMPLE:

The present study is proposed as a pilot study due to the absence of similar studies in this field that allow a

calculation of the adjusted sample size. For this, 80 participants will be included, who must meet the established selection criteria.

CRITERIA FOR SELECTING THE PARTICIPANTS

INCLUSION CRITERIA.

- Healthy people
- Be enrolled in a degree in health sciences at the partner universities in the study in the first year.
- Optimal cognitive abilities and mentally competent to participate in the study.
- In cognitive conditions to complete the study questionnaires
- Have an optimal command of the Spanish language to complete the questionnaires.
- Signing of the informed consent for participation

EXCLUSION CRITERIA.

- Present some of the contraindications for a treatment with NESA X SIGNAL®: Pacemaker or other electrical surgical device, internal bleeding, do not apply electrodes on skin in poor condition, with ulcerations or wounds, acute febrile processes, pregnancy, acute thrombophlebitis and / or phobia of electricity, and pregnant.
- Combine another pharmacological treatment that influences the variables to be evaluated during the study.

ELIMINATION CRITERIA.

- Missing an intervention session of the 10 scheduled sessions.

RECRUITMENT OF PARTICIPANTS AND EVALUATION PROCESS.

Phase 1. Dissemination of the study

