1. SLEEP VARIABLES

1.1 Perceived sleep quality: through a validated sleep quality perception questionnaire, Pittsburgh questionnaire (Escobar Córdoba & Eslava Schmalbach, 2005) (ANNEX 04)

1.2 Salivary cortisol measurement: Through the Soma OFC II cube. The analysis will be performed in real time through the collection of saliva, it is not affected by recent food and drink; Once the swab is in the buffer, your sample is stable for months. It is a validated instrument (Fisher, 2015).

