No risk is foreseen during the performance of the technique. The study will meet the ethical requirements of the Helsinki Declaration of the World Medical Assembly (WMA) on ethical principles for medical research involving human beings.

Provision of measures to minimize pain, stress, physical or emotional risk.

Study participation does not have harmful risks to health. No study complications and no adverse effects of the applied techniques are anticipated. They will be warned in advance that during the first two sessions of the treatment they could perceive slight alterations of the sleep phases, exceptionally.

Forecast of remuneration or gratification for participation in the study

The study subjects have as a common link their own health or that of the future patient, therefore, all of them can benefit from knowing the applicability of the proposed technique in improving the quality of life. No economic remuneration is foreseen, however, the student will be rewarded with a special recognition in the subjects that he / she takes related to research methodology.

Sensitivity to the needs and perspectives of the people participating in the project

No long-term benefit or harm is anticipated, as the technique is safe and tested in healthy patients.

Provision of contracting liability insurance

The different Faculties have civil liability insurance that will cover possible liabilities.

SCHEDULE

The total duration of the project is estimated to be 8 months.

- A. Project design.
- B. Authorization of the Center and request for approval by the Ethics Committee for Clinical Research.
- C. Recruitment of Personnel and Users.
- D. Therapeutic intervention and data collection.
- E. Statistic analysis.
- F. Evaluation and interpretation of results.
- G. Drafting of results report and dissemination of results.

	M AND S AND S							
CHORES	1	2	3	4	5	6	7	8
TO								
B								
C								
D								
AND								
F								
G								

QA

1.- Identification of collectors:

Each collector will be assigned a code that will be included as the first digit in the patient's identification code in the 1-xxxx format. Each collector is responsible for the data dump so the collector digit matches the data dump.

Recorder	Code
Person I	1
Person II	2

Person III	3
Person IV	4

2.- Quality audits:

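### The plan warns of early sleep disturbance but schedules no adverse-event recording and no assessment during the five treatment weeks, so transient and individual harms go unrecorded

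*Combined protocol and SAP*

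**What the plan says.** Under the heading on measures to minimise pain, stress and risk, the protocol states "Study participation does not have harmful risks to health" and "No study complications and no adverse effects of the applied techniques are anticipated". It then says participants will be warned that "during the first two sessions of the treatment they could perceive slight alterations of the sleep phases, exceptionally". A little further on it adds "No long-term benefit or harm is anticipated, as the technique is safe and tested in healthy patients".

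The section defining the study variables lists a sleep questionnaire ("1.1 Perceived sleep quality: through a validated sleep quality perception questionnaire, Pittsburgh questionnaire"), salivary cortisol, two academic stress questionnaires, sociodemographic data and the first-semester grade. On timing it says "The variables will be measured before the start of the intervention (PRE), at the end of the intervention (POST) and one month after the end". Both arms are assessed alike. Treatment is two 60-minute sessions a week for five weeks; controls receive no device application.

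Under Elimination Criteria the only entry is "Missing an intervention session of the 10 scheduled sessions". The statistical analysis plan describes between-group and within-group comparisons of the listed variables. Neither it nor the audit list in the QA section has an adverse-event item.

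**The concern.** The risk section expects no adverse effects and also names one that treatment might cause. That effect concerns sleep, which is part of the trial's main goal. The participants are healthy first-year students, and the trial is motivated by exam stress. The text describes no means of recording that effect or any other.

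At stake is what the trial can say about tolerability when it ends. Followed as written, it would hold no systematic harms data. The gap could not be filled later either, because the database is to be erased after about two months of coding and analysis, with only statistical data kept.

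**Working it through.** The plan gives no figure on harms to reproduce. The check sets the schedule against the warned effect and then sizes what the planned data can and cannot show.

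**Inputs.** 80 participants (sample-size section). Four sites of 20 and two balanced arms (random assignment section): 4 × 20 = 80, and 80 / 2 = 40 per arm. Two sessions a week for five weeks: 2 × 5 = 10. Significance level 0.05 (analysis section); sidedness is not stated, so two-sided is assumed.

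**Timing.** At two sessions a week, the first two sessions fall in week 1. The nearest assessments are PRE, before treatment starts, and POST, at the end of week 5. No measurement lies in the window to which the warning refers.

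**What the Pittsburgh comparison can show.** The detectable difference in SD units at 80% power is (1.96 + 0.84) × √(1/n₁ + 1/n₂).

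- 40 and 40: 2.80 × √(2/40) = 0.63 SD.
- Treated arm reduced to 36 (illustrative): 2.80 × √(1/36 + 1/40) = 0.64 SD.
- Treated arm reduced to 32 (illustrative): 2.80 × √(1/32 + 1/40) = 0.66 SD.
- Both arms reduced to 32: 2.80 × √(2/32) = 0.70 SD.

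With 40 per arm, power by the normal approximation is 27% at 0.3 SD, 61% at 0.5 SD and 95% at 0.8 SD. The t distribution gives 26%, 60% and 94%. A moderate to large sustained shift in the mean would probably be seen. A short-lived change, or a change in a few students, would not.

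**What recording would add.** If events were recorded in all 40 treated students, the chance of seeing at least one is 1 − (1 − p)^40.

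| True event rate p | Chance of at least one event |
|---|---|
| 1% | 33% |
| 2% | 55% |
| 5% | 87% |
| 10% | 99% |

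If none occurred, the exact upper 95% limit is 1 − 0.05^(1/n) one-sided and 1 − 0.025^(1/n) two-sided.

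| Treated n | One-sided | Two-sided |
|---|---|---|
| 40 | 7.2% | 8.8% |
| 36 | 8.0% | 9.7% |
| 32 | 8.9% | 10.9% |

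**Elimination rule.** Controls have no sessions to miss, so the rule can remove only treated students, and the plan does not ask for the reason. As an illustration, a 5% event rate gives 0.05 × 40 = 2 affected students. If both skipped a session, the randomised group would show 2/40 = 5% and the retained group 0/38 = 0%. This shows the direction of a possible bias. The documents give no figure for how often it would happen.

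**The case against.** The strongest reply is that the trial does measure harm to sleep. The Pittsburgh questionnaire is taken in both arms at three times, and nothing limits the comparison to improvement. This stands. A reader might infer that the plan cannot detect harm in its main domain at all, and the documents do not support that. What it misses is the transient early disturbance and the individual event.

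A reader might also infer that the plan declares adverse effects absent, or sets out to prove safety. It does neither. It says none are anticipated, and the warning is qualified as slight and exceptional. The statement that "the technique is safe and tested in healthy patients" is a premise, and safety is not among the objectives.

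Nor do the documents show that eliminated students are the ones who were harmed. Students miss sessions for many reasons, and the plan links none of them to side effects. Only a possible bias can be claimed. Exclusion for one missed session is also an analysis-population question in its own right and should not be counted again here.

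Finally, the information sheet is said to cover risks and a contact route at each centre, so spontaneous reports are possible. The audit list mentions drug use and perceived health, which the variable section does not define, so the visible list may be incomplete. Neither is planned adverse-event recording, but absence can be asserted only for the protocol body.

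**Conclusion.** The concern holds in a limited form. The risk statements are in tension with each other. In the protocol body, no adverse events are recorded and nothing is assessed during the five treatment weeks. The one effect the plan foresees falls where nothing is measured.

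The existing sleep scores protect only against sustained average worsening, with about 80% power at 0.63 SD. This assumes 40 per arm, a two-sided 0.05 test and no losses. The elimination rule could hide harm in the treated arm if side effects lead to absences.

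This is more than a missing detail, because the plan carried out exactly as written yields no harms data. It does not threaten the planned efficacy comparison as such. Recording would have a modest yield: no events in 40 would still be compatible with a rate of about 7% to 9%.

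**What to change.** - Add one short, neutrally worded open adverse-event question on the Google Forms platform already planned. Ask both arms on the same schedule: week 1, later treatment weeks, POST and one month.
- Log the reason for every missed session.
- Report counts by arm with exact confidence intervals for everyone randomised, including those eliminated.
- Reconcile the statements in the risk section so that the expectation and the warning agree, and state that the trial describes tolerability and does not test safety.

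**Cost.** One form and one table. If sent weekly, this is at most 5 + 2 = 7 brief forms per participant, or 7 × 80 = 560 responses. Treatment, sample size and planned outcome analyses are unchanged. Controls receive no device application and will know their arm, so self-reported harms are open to expectation effects. Repeated prompts that name sleep could also colour the sleep questionnaire, which is why the question should be open and neutral. Asking only at treatment sessions would be lighter but would question the arms unequally.
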